## **7. SELECTION OF PROCESS OF PARTICIPANTS**

### **7.1 Number of Participants Planned**

Based upon the anticipated event rates, premature treatment discontinuation and expected relative efficacy, approximately 70 participants will be enrolled in the study, with approximately 70 participants in each arm.

### **7.2 Inclusion Criteria**

- Previously diagnosed with cystic fibrosis (mild, moderate or severe)
- Prescribed (licensed medical provider) airway clearance device/system for at home, self-treatment for airway clearance
- Physically able to perform self-treatment or treatment by an at home medical provider

### **7.3 Exclusion Criteria**

- History of tobacco use
- History of excessive alcohol consumption, more than 2 drinks per day, 10 per week
- Any other medical condition that would preclude use of an airway clearance device
- Previously diagnosed with major cardiological disease

#### **7.3.1 Related to General Patient Characteristics**

1. Presence of any severe medical or psychological condition that, in the opinion of the Investigator, would compromise the participant's safe participation.
2. Immunocompromised by other types of viral infections or has a history of any other hepatitis form e.g. types A, C, D, E.
3. Underlying diseases or other dermatologic conditions that require the use of interfering topical or systemic therapy or that might interfere with study assessments such as, but not limited to, atopic dermatitis or herpes zoster (shingles). This includes clinically significant abnormal findings, uncontrolled or serious disease, or any medical or surgical condition, that may either interfere with the interpretation of the clinical trial results, and/or put the subject at significant risk (according to Investigator's judgment) if he/she participates in the clinical trial.
4. The subject has received, applied or taken some specified treatments within the specified timeframe prior to the Baseline visit
5. The subject is unwilling to refrain from use of prohibited medication during the Clinical Trial.
6. N/A
7. Presence of any condition (medical, psychological, social, or geographical), actual or anticipated, that the Investigator feels would restrict or limit the participant's successful participation for the duration of the study.

8. Receipt of any investigational treatment (medical device or drug) within 30 days prior to baseline visit.

9. Previous participation in a Electro Flo 5000 medical device study.

10. Known allergy to any components of the device itself (e.g. plastics/polymers).

### **7.3.2 Related to Other Conditions**

None

## **8. TREATMENTS**

### **8.1 Medical Device Description**

The Electro Flo 5000 is intended to assist in airway clearance therapy when the physician's choice of therapy is external manipulation of the thorax. Additionally, the Electro Flo 5000 is indicated for external manipulation of the thorax to promote airway clearance and improve bronchial drainage.

### **8.2 Description of Blinding Methods**

Final data analysis shall be completed by a third party, data analysis and reporting agency.

### **8.3 Method of Assigning Participants to Treatment Group**

N/A - All included shall be assigned to the single arm.

### **8.4 Packaging and Labeling**

Please see User Manual and instructions along with physician prescription.

### **8.5 Storage Conditions**

Please see User Manual

## **8.6 Access to the Randomization Code During the Study**

N/A for this trial

The Investigator will be supplied with participant information if medically needed or required for safety from the Sponsor.

Additional unblinding materials will be available and are to be kept in a safe place at CRU level (or subcontractor, if any) throughout the clinical trial. The Sponsor will retrieve all envelopes, whether opened or sealed, on study completion.

In case of a Serious Adverse Event, the code should be broken only in exceptional circumstances when knowledge of the Investigational Product is essential for treating the patient.

In case the physician at the investigational site believes unblinding is needed, he/she must first contact the Medical Advisor located at Mack Biotech for further direction. All calls will be documented as appropriate to include date and time of the call, name of the Optional Study Group Medical Advisor, name, qualification, and address of the physician contacting Optional Study Group, patient ID, documentation of the request, and decision for unblinding or not.

If possible, a contact should be initiated with the Monitoring Team before unblinding. In case the decision to unblind is made, the Investigator must document it with the date, time of day, and reason for unblinding, and report this information in the appropriate page of the CRF and source document.

Note that when documenting the reason for unblinding, the Investigator must not provide any detail regarding the nature of the Investigational Product. The Investigator should not divulge medication detail to any Med Systems, Inc., or Mack Biotech, Corp. staff member, Sponsor's representative, or to any Study Committee members until database closure. Furthermore, when completing forms (eg, AE, SAE), the study treatment should not be disclosed on the forms. The unblinding envelopes will be sealed again and stored at the site level until the end of the study (envelopes opened by the CRU or a subcontractor must also be sealed again).

## **8.7 Responsibilities**

The Investigator or other personnel allowed to store and dispense Investigational Product (IP) will be responsible for ensuring that the IP used in the study is securely maintained as specified by the Sponsor and in accordance with the applicable regulatory requirements.

All IP shall be dispensed in accordance with the Investigator's prescription and it is the Investigator's responsibility to ensure that an accurate record of IP issued and returned is maintained.

Any quality issue noticed with the receipt or use of an IP (deficient IP in condition, appearance, pertaining documentation, labeling, expiry date, etc) should be promptly reported to the Sponsor, who will initiate a complaint procedure.

Under no circumstances will the Investigator supply IP to a third party, allow IP to be used other than as directed by this Clinical Trial Protocol, or dispose of IP in any other manner.

## **8.8 Retrieval and/or Destruction of Investigational Product**

All partially used or unused treatments will be retrieved by the Sponsor. A detailed treatment log of the returned IP will be established with the Investigator (or the pharmacist) and countersigned by the Investigator and the Monitoring Team.

The Investigator will not destroy unused IP unless the Sponsor provides written authorization to the contrary.

A potential defect in the quality of IP may be subject to initiation by the Sponsor of a recall procedure. In this case, the Investigator will be responsible for promptly address any request made by the Sponsor, in order to recall IP and eliminate potential hazards.

## **8.9 Concomitant Treatment**

None

### **8.9.1 Prohibited Concomitant Treatment**

None

### **8.9.2 Permitted Concomitant Treatment**

Any medical devices other than those listed above are allowed, and should be administered, as necessary for the treatment of the patient, when possible with a stable dose, at the discretion of the Investigator. All treatment with these medical devices should be recorded on the appropriate CRF.

### **8.10 Treatment Compliance**

Compliance is assessed by counting the number of returned bottles if any at each visit. The Investigator (or delegate) must complete the appropriate pages of the treatment log form and of the CRF. A discontinuation is defined as a period with a least three consecutive days without study medical device intake.

The study shall be open enrollment but patients must have access to the clinical location for clinical survey reporting. The survey must be completed two (2) times per week during the 21 day long trial. Potential participants should reside in the United States.

The monitor supervising the study will verify the data by comparing the recorded data with the investigational product retrieved.

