## **4. INTRODUCTION AND RATIONALE**

### **4.1 Role of the Electro Flo 5000**

#### **4.11 Introduction**

The Electro Flo 5000 Airway Clearance System is a therapy for the directing application of a percussive force to the chest wall to loosen mucus. The system is comprised of: (1) a Self-Administrator -- a self-applicator assembly including a first strap overlaying and substantially coextensive with a second strap, wherein the first and second straps are joined at their respective ends, and a pouch disposed between the first and second straps for directing the pulse generated by the percussor to the body; and (2) the Electro Flo 5000 Force Multiplying Percussor -- consisting of a hammer and anvil having a force-receiving surface and a force-delivering surface energized by an electric current and pulse generator. (See Attachment 1) Rapidly repeated impulses to the chest by the electronically cycled percussive hammer dislodges mucus adherent to airways within the lungs. Strategic placement of the system permits focused treatment of the affected lung regions. Patients apply the device directly to their frontal thorax or to their back by securing the device in the Self-Administrator and focusing the pulse where relief is desired. Users can apply Airway Clearance Therapy (ACT) directly on their back without the aid of another person.

The Electro Flo 5000's Force Multiplying Technology allows users to control the pulse frequency and pulse force of the impact through a combination of 30 independently adjustable settings. There are five power and six speed settings. The Electro Flo 5000's pulse force ranges from 15 to 35 pounds.

The broad range in pulse force and greater power of the Electro Flo 5000 is a function of its unique design. The device is comprised of over 200 parts constructed from specialized machined magnetic material and high-impact molded plastics.

The Electro Flo 5000 Airway Clearance System is an integrated approach to delivering care that is responsive to a patient's specific needs. It is a high-quality, high-value, cost-effective therapy.

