## **12.3 Description by Type of Visit**

- Baseline enrollment form completed and submitted online (secure site), informed consent signed and submitted.
- Follow up call, email and follow up summary completed by the Investigator at the end of the one month treatment period with written results.
- Three (3) month participant courtesy email to confirm safety and answer any questions.

**There is no strict timing for the phone calls. In any case, it is better to call the patient after a delay, than to not call them at all (even in this case, the phone call record page of the CRF should be completed).**

The patient visit schedules will be given by the Investigator as soon as the participant is randomized, so as the Investigator can plan in advance all the necessary appointments with the participant.

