#### **13.6.1.2 Measurement of Treatment Compliance**

Treatment compliance for each patient will be calculated as the number of days study medical device was actually used (ie, number of days on treatment minus days of temporary discontinuation) divided by the number of days of follow-up, allowing for early permanent discontinuation of study medical device when applicable. Study medical device discontinuation is defined as a minimum of 3 consecutive days without study medical device intake. The percentage of participants at least 80% compliant will also be reported.

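### Compliance is to be measured by counting returned bottles, which a reusable percussor does not have, so the stated method cannot supply the days of use or the 80% compliance result

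*Protocol*

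**What the plan says.** Protocol section 8.10 sets the method: "Compliance is assessed by counting the number of returned bottles if any at each visit". The investigator or a delegate fills in a treatment log and CRF pages, and the section adds: "The monitor supervising the study will verify the data by comparing the recorded data with the investigational product retrieved". It also defines a discontinuation as at least three consecutive days without the device.

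Section 13.6.1.2 defines the result. The numerator is the "number of days study medical device was actually used (ie, number of days on treatment minus days of temporary discontinuation"), and this is "divided by the number of days of follow-up, allowing for early permanent discontinuation of study medical device when applicable". The same section states: "The percentage of participants at least 80% compliant will also be reported".

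The product is described in section 4.11 as a percussor with a self-applicator strap: "The device is comprised of over 200 parts constructed from specialized machined magnetic material and high-impact molded plastics". The SAP does not mention compliance.

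**The concern.** The method in 8.10 reads as if written for a dispensed drug, where returned containers say something about doses taken. A percussor is handed over once and handed back once. If the text is followed, the compliance field carries no information on use, and the monitor's comparison with the returned product adds none.

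This matters because treatment is self-administered at home and section 4.3 makes each participant his or her own comparison. A reader of a before/after change will want to know whether, and on how many days, the study device was used. The protocol promises an answer, the percentage at least 80% compliant, that its stated method cannot produce.

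**Working it through.** The 80% cut-off is a chosen threshold, so there is no derived figure to reproduce. The check is whether what is collected can feed what is reported.

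**1. Method against quantity**

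- Needed (13.6.1.2): days of use per participant, and runs of three or more days without use.
- Collected (8.10): a count of returned bottles, treatment-log and CRF pages, and a comparison with retrieved product.
- Product (4.11): a reusable device and strap. No bottle, consumable, use counter or data download is described.
- Treatment log: section 8.8 describes a log of returned product. No daily-use field is specified anywhere.

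**2. What the count can distinguish**

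With a 21-day period (sections 6.2 and 8.10), the threshold is 0.80 × 21 = 16.8, so 17 days:

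- 17/21 = 81.0%, compliant
- 16/21 = 76.2%, not compliant

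The measure has to separate 16 days from 17. The bottle count is zero or not applicable for 1 day of use, 21 days, or anything between.

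**3. Other data that might serve**

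- Visits: section 12.3 lists an online baseline form, a call, email and summary "at the end of the one month treatment period", and a three-month email. It lists no on-treatment visit.
- Survey (8.10): two per week over three weeks is 2 × 3 = 6 contacts. The survey is not assigned to record device use.
- Smart-device data (8.11): sent for the two objectives, which are oximetry and spirometry before and after treatment (5.1, 5.2). These are not named as a compliance source either.
- Section 7.2 requires a prescribed airway clearance device or system without saying that it is the study device, and section 8.9.2 permits other devices. A submitted reading therefore does not by itself show that the study device was used.

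**4. Why days of use should be counted directly**

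The bracketed formula in 13.6.1.2 subtracts only days of temporary discontinuation, meaning gaps of three or more days. Divide 21 days into 21/3 = 7 blocks of three. With no three-day gap, each block must contain at least one day of use, so the minimum is 7 days. Use on every third day achieves it. The formula scores this (21 − 0)/21 = 100%, while actual use is 7/21 = 33.3%. Even a good daily record would be lost if passed through that formula.

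**5. The denominator**

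The treatment period is 21 days in 6.2 and 8.10 and one month in 12.3. The reimbursement cap in 8.11 implies 210/7 = 30 paid days, against 21 × 7 = $147 for 21 days. Taking one month as 28 to 31 days (assumed), 80% requires 23 to 25 days of use (0.80 × 28 = 22.4; 0.80 × 31 = 24.8). A participant treated on exactly 21 days would score 21/28 = 75.0% down to 21/31 = 67.7%. If days of follow-up means the two months in 6.2 (assumed 56 to 61 days), the score is 21/56 = 37.5% down to 21/61 = 34.4%.

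**The case against.** The best defence is that the bottle wording is template residue and that use will be known by other means. Several parts of this stand.

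- A reader might infer that participants are not seen during treatment. The documents do not support that. Section 8.10 requires access to the clinical location for a twice-weekly survey, section 12.3 promises visit schedules it does not set out, and Appendix 1 has the sponsor generate them. What can be said is that 12.3 lists no on-treatment visit and that the survey is not assigned to record use.
- A reader might infer that use can be known only by recall at the end. That is too strong. Before/after readings are to be sent during treatment, and each pair is some evidence of a session. The gap is that these data are not designated as the compliance source and do not identify which device was used. Sections 4.18 and 13.6.2 discourage other devices or therapy but do not exclude them.
- A reader might infer that the exposure summary in 13.6.1.1 also fails. It rests mainly on start and stop dates, and section 11.1 records the reason for discontinuation on the CRF, so that failure is not shown.
- The device might hold a usage record: section 2.0 calls it programmable, and details are left to a User Manual that was not available for this review. None is described in the protocol, and none is named as a source.
- The content of the CRF pages is not shown. They could hold a use field, but the protocol does not call for one.

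None of this rescues the stated method. The words allowing that there may be no bottles put nothing in their place.

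**Conclusion.** The point holds. As written, the method in 8.10 cannot supply days of use, the percentage at least 80% compliant, or the three-day gaps that define discontinuation. This is a stated rule that fails for this product, not merely missing detail.

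Its reach is limited. Section 13.4.1.2 puts all efficacy and safety analyses on the intention-to-treat population irrespective of compliance, and no per-protocol or compliance-adjusted analysis is planned. The damage is to the descriptive compliance results and to how before/after changes can be read. It should be corrected, but it does not threaten the main analysis.

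A reader might express the size as 70 × 21 = 1,470 device-days without a valid measure. That product takes 21 days as settled, which the documents do not allow (30 days would give 70 × 30 = 2,100), and it is not an effect on any result. The useful statement is that the stated measure carries no information on use for any of the 70 participants.

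The conclusion assumes only that the product has no countable supply and that no usage record is read from it. The 17-day threshold also assumes a 21-day denominator.

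**What to change.** - In 8.10, replace the bottle count with a dated entry, in the existing smart-device report, on whether the study device was used and in how many sessions. Require it for every treatment day, not only days on which readings are sent.
- Have the twice-weekly survey ask about study-device use on any day not reported.
- In 13.6.1.2, name these two records as the source, and count days of use directly from them instead of subtracting only gaps of three or more days.
- Have the monitor verify compliance against the time-stamped submissions. Keep product retrieval for accountability only, since sections 8.8 and 16.2 still require it.
- Reconcile the treatment period in 6.2 and 8.10 with that in 12.3, and state which days form the compliance denominator.

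The cost is protocol wording, one short item per day in a report participants already send, and one survey question. Use would still be self-reported, but recorded during treatment and tied to the study device.

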### **8.11 Participant Reimbursement**

Participants shall be reimbursed at a rate of seven dollars (\$7.00) per day for each day that data for the two objectives is sent to the Principal Investigator. The reimbursement is provided for the participant's time for recording the data on a personal smart device, the cost of data transfer and overall phone costs for sending the information to the Principal Investigator. The total reimbursement amount that may be provided to the participant is no more than \$210.00. The reimbursement shall be provided to the participant, by the Sponsor, after the participant completes the trial period by company check paid to the participant.

## **9. ASSESSMENT OF INVESTIGATIONAL PRODUCT**

### **9.1 Efficacy**

The goal of this trial is to illustrate before and post treatment changes measured by spirometer.

### **9.1.1 Efficacy Criteria**

Primary: Physical exam by medical practitioner for initial diagnosis and changes in spirometer reading from before treatment compared to reading three (3) hours after treatment. In addition, changes in iHealth Air pulse oximeter (FDA 510k K131111) reading from before treatment compared to reading three (3) hours after treatment.

#### **9.1.1.1 Primary Criterion**

Composite success rate. Safety - no issues or reported adverse conditions.

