#### **9.1.2.1 Definitions of Components of the Primary Efficacy Endpoint**

N/A

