## **10. PATIENT SAFETY**

### **10.1 Adverse Events Monitoring**

#### **Definitions:**

An adverse event is any untoward medical occurrence in a clinical investigation participant administered a medical device and which does not necessarily have to have a causal relationship with this treatment.

A Serious Adverse Event is any untoward medical occurrence at any dose that:

- Results in death or;
- Is life-threatening or;  
Note: The term "life-threatening" in the definition of "serious" refers to an event in which the patient was at risk of death at the time of the event; it does not refer to an event that hypothetically might have caused death if it were more severe.
- Requires inpatient hospitalization or prolongation of existing hospitalization or;
- Results in persistent or significant disability/incapacity or;
- Is a congenital anomaly/birth defect;
- Is a medically important event:  
Medical and scientific judgment should be exercised in deciding whether expedited reporting is appropriate in other situations, such as important medical events that may not be immediately life-threatening or result in death or hospitalization but may jeopardize the patient or may require intervention to prevent one of the other outcomes listed in the definition above. These should also usually be considered serious.

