## **Adverse Events**

All Adverse Events regardless of seriousness or relationship to Investigational Product, including those from the first visit planned in the Clinical Trial Protocol/signature of the informed consent form, are to be recorded on the corresponding page(s) included in the Case Report Form. Whenever possible, symptoms should be grouped as a single syndrome or diagnosis. The Investigator should specify the date of onset, intensity, action taken with respect to Investigational Product, corrective treatment/therapy given, outcome and his/her opinion as to whether there is a reasonable possibility that the Adverse Event was caused by the Investigational Product.

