#### **13.7.1.1 Description of the Primary Variable(s)**

The primary efficacy endpoint is the composite cluster of the first occurrence, over the duration of study (randomization to study end date inclusive), of the following adjudicated events:

- Any skin conditions caused by the device to include irritations,
- Any allergic reactions,
- Any new medical conditions during the study.

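### The primary efficacy criterion asks for no adverse conditions but has no attribution rule, unit, threshold or window, so in a single arm of people with cystic fibrosis it reflects background illness rather than the device

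*Protocol*

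**What the plan says.** Under Efficacy Criteria, Protocol 9.1.1.1 states the primary criterion in two fragments: "Composite success rate. Safety - no issues or reported adverse conditions". The section meant to explain it, 9.1.2.1 ("Definitions of Components of the Primary Efficacy Endpoint"), is marked not applicable. The SAP adds no definition.

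On attribution, Protocol 10.1 defines an adverse event as one that "does not necessarily have to have a causal relationship with this treatment" and requires recording of "All Adverse Events regardless of seriousness or relationship to Investigational Product". Protocol 13.7.1.1 defines the primary efficacy endpoint as the first of three kinds of adjudicated event. Skin conditions count only if the device caused them. Allergic reactions count without that limit, and so does "Any new medical conditions during the study". Under 13.7.1.2.3, events after permanent discontinuation of the device still count. The analysis is Kaplan-Meier curves, a log-rank test, and the number and percentage of participants with an event.

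On design, "approximately 70 participants will be enrolled in the study" (7.1) and "All included shall be assigned to the single arm" (8.3). Participants have cystic fibrosis of any severity (7.2). Section 4.3 relies on before/after measurement in place of a control.

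Other sections name different primary measures: SpO2 change (5.1), spirometry and oximetry change (9.1.1, 9.1.2), and a reduction in the appearance of cystic fibrosis (13.7, 13.7.1).

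**The concern.** People with cystic fibrosis fall ill for reasons unrelated to a percussor. A rule that counts any adverse condition, with no attribution limit and no control arm to show the background rate, cannot separate the disease from the device. Placed inside the efficacy criterion, it lets unrelated illness lower or defeat the efficacy result. It also says little about device safety, because device-related events are mixed with all the others.

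Since unit, threshold and window are all left open, the same data could be reported as a success or a failure depending on the reading adopted. For a primary criterion that must be settled in advance.

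**Working it through.** **Inputs**
- n = 70, one arm (Protocol 7.1, 8.3).
- p = probability that a participant has at least one counted event of any cause. The documents give no value, so a range is assumed.
- Window: 21 days of active participation, or follow-up to a common end date about two months after the last participant enters (both in 6.2). Section 13.7.1.1 counts to the study end date.
- Success threshold: none stated.

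The only design figure is 70. Section 13.2 supports it with no event rate, threshold or power, so there is no figure of the plan's own to reproduce on this point.

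**Step 1. Participant-level reading.** If success requires freedom from any adverse condition as well as clinical benefit, then P(success) ≤ 1 - p, with equality only if every event-free participant benefits.

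**Step 2. Trial-level reading.** If no participant may have an event, P(criterion met) = (1 - p)^70, assuming independent participants with a common p.

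| Assumed p | Highest possible success rate (step 1) | Chance of zero events in 70 (step 2) |
|---|---|---|
| 1% | 99% | 0.99^70 = 49% |
| 2% | 98% | 0.98^70 = 24% |
| 5% | 95% | 0.95^70 = 2.8% |
| 10% | 90% | 0.90^70 = 0.06% |
| 20% | 80% | about 0 |
| 30% | 70% | about 0 |

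Solving (1 - p)^70 = 0.05 gives p = 1 - 0.05^(1/70) = 4.2%. Solving for 0.01 gives 6.4%. So the chance of meeting a zero-event rule drops below 5% only if p exceeds 4.2%, and below 1% only if p exceeds 6.4%.

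**Step 3. Effect of the window.** Take a constant hazard giving p = 5% in 21 days. Over 61 days (two months), p = 1 - 0.95^(61/21) = 13.8%, and the chance of zero events in 70 falls from 2.8% to 0.003%. Starting from 1% in 21 days, p becomes 2.9% and the chance falls from 49% to 13%.

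**Step 4. What a perfect result shows.** For 0/70 the exact two-sided 95% upper limit is 1 - 0.025^(1/70) = 5.1%. A zero count bounds the rate at about 5%; it does not show that the rate is nil.

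**Step 5. How much a missing threshold matters.** Suppose the participant-level rule required at least 80% success, that is 56 of 70. This threshold is illustrative and not in the documents. With a device that helps everyone, the binomial chance of reaching it is 99.7% at p = 10%, 57.1% at 20% and 4.1% at 30%. The outcome is then decided entirely by background illness.

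**The case against.** A reader might infer that the primary criterion is almost certain to fail whatever the device does. The documents do not support that. Section 9.1.1.1 speaks of a success rate, and 13.7.1.2.3 reports a percentage of participants; both point to the participant as the unit, and a rate does not fail because some participants have events. No passage says that one event fails the trial, and no threshold exists against which to fail. Near-certain failure needs the zero-event reading and also a background rate above about 4 to 6%, which the documents do not give. On the participant-level reading at p = 5%, the cap is a mild 95%.

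Other points on that side:
- Section 9.1.1.1 says adverse conditions, not adverse events as defined in 10.1. Section 10.3 and Appendix 5 treat outcome events as separate from adverse events. So the any-cause reading of 9.1.1.1 is an inference. It stands because 9.1.1.1 sets no limit and because 13.7.1.1 limits one component to the device but not the other two.
- The full stop in 9.1.1.1 allows the safety fragment to be a separate statement. It still sits under the primary efficacy criterion, and 13.7.1.1 makes harms the primary efficacy endpoint in any case.
- Primary events are adjudicated (6.4, Appendix 4). But no attribution rule is given to the adjudicators for non-fatal events, so adjudication does not remove unrelated illness.
- Section 13.8.1.2 already plans a table of any adverse event and mentions device-related summaries. That makes the repair easier; it does not take the events out of the efficacy criterion.

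**Conclusion.** The point holds. The defect is a criterion that admits events of any cause and leaves unit, threshold, window and attribution undefined, in a design with nothing to separate disease events from device events. It is not a demonstration that the trial must fail.

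The size depends on the reading and on p. The participant-level ceiling runs from 99% at p = 1% to 70% at p = 30%. The chance of satisfying a zero-event rule runs from 49% at 1% to 0.06% at 10%, and is lower if events are counted over the longer follow-up. All these figures rest on assumed rates; the zero-event and threshold probabilities also assume independent participants with a common rate. The qualitative conclusion needs neither assumption: under either reading, illness unrelated to the device lowers the result. Because this is the primary criterion, it should be corrected before the plan is used.

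**What to change.** 1. Remove adverse events from the efficacy criterion in Protocol 9.1.1.1 and from the primary efficacy variable in 13.7.1.1. Revise 13.7.1.2.1 to 13.7.1.2.5 to match, since the censoring rule, log-rank test and Cox subgroup models serve the event composite.
2. Leave an efficacy criterion in 9.1.1.1: the before/after SpO2 change already named in 5.1. Reconcile 9.1.1, 9.1.2, 13.7 and 13.7.1 with it, including the post-treatment time, which is up to 3.5 hours in 5.1 and three hours in 9.1.1. If any composite is kept, state its unit, threshold, window and attribution rule.
3. Report safety separately as the proportion of participants with a device-related adverse event, using the investigator's relationship opinion already collected under 10.1, with an exact 95% confidence interval and no requirement that it be zero.
4. Keep a descriptive table of all-cause adverse events.

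The cost is wording in the Protocol and SAP, including a rewritten primary analysis section; no new data item is needed for attribution. The drawback is that relationship is the investigator's judgement in an uncontrolled trial, so the all-cause table must stay beside the device-related proportion.
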